The interventions will be described in accordance with the TIDieR (Template for Intervention Description and Replication) Checklist²⁶ (see www.equator-network.org). The TIDieR checklist has been recommended for use in conjunction with the SPIRIT statement as an extension of Item 11¹.

Participants in both groups will attend 4 x 60-90 minute, one-on-one sessions with a Physiotherapist at weekly intervals and will be provided with OA and physical activity education on top of a graded walking program. This treatment dosage reflects what was used in our knee OA pilot study and in many chronic back pain RCTs of Explain Pain. Following completion of the one-on-one sessions, participants will perform 4 weeks of at-home workbook activities combined with further progression of a graded walking program.

Both of the intervention groups will receive the following:

- A standard knee assessment (subjective and objective)
- Provision of general information about knee osteoarthritis and physical activity
- Discussion of knee x-ray findings (note: content will differ significantly between groups)
- Guidance regarding graded progression of a walking program
- Individualised goal setting
- At home workbook activities (over 4 weeks) with weekly check-in phone calls by the treatment clinician.

Graded walking program and goal setting:

Participants in both groups will be guided to measure their baseline walking tolerance (i.e. how far, on average, they are able to walk before their pain level increases). They will then reduce this time/distance by 20% - with this activity level becoming their 'start' walking level. Participants will be guided to set a weekly program (beginning at this 'start' level) and then plan gradual weekly increases at a rate of approximately 10% each week. Participants will also be guided to set activity-related short and long-term goals. One of these goals will be a walking goal (if appropriate) – such that the 'pacing' approach can be demonstrated and practiced.

In addition, participants in each group will receive the following during the one-on-one session and the 4 week at-home intervention:

1. One-on-one sessions:

Explain Pain Group:

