
Doing regular physical activity can help to reduce your pain, strengthen your muscles, maintain your joint function and improve your sleep and overall health.
	
3
	
Regular physical activity has countless health benefits (at any age) and enhances bioplastic change in your whole system. This helps make your system less sensitive = able to do more with less pain. There is very strong evidence that activity and exercise are safe and do not lead to further structural damage.
	
3 & 4

It is normal to feel some pain in your muscles when you start an exercise program or new activity. However, if pain feels unusual or severe, or lasts for more than 2 hours after you have stopped, it is probably best to avoid or change that activity.
	
3 & 4
	
Understanding what pain means can powerfully influence pain. It is often not necessary to stop an activity if it is painful. Your own brain can make powerful medications to reduce pain.
	
All

Table 3: Educational topics in the Usual care [standard education] control group and enhanced education provided in the Explain Pain intervention group

Treatment component	Interventions - Graded walking program combined with:		Timing Considerations
	Standard Education + Sham US (Control)	Enhanced education (Explain Pain)	
Session 1			To more closely match treatment duration and therapist time between groups, the Control group will have: 1. Increased time taken for the Standard physiotherapy assessment (go slow!) 2. Inactive ultrasound application
Baseline assessment	Standard physical examination Standard subjective examination	Standard physical examination Enhanced subjective examination ('standard' + identification of participants' education targets for EP).	
Education	General education Provide inactive ultrasound to 4 locations on the most painful knee (~5 mins each). Introduce participants to the AA handbook (to take home)	Enhanced education Introduce participants to 'Explain Pain Handbook' and the 'The Protectometer' (to take home)	
Graded walking program	Instructions for following week re: Establish baseline walking tolerance that does not result in sustained, increased pain following walking (for next session)		

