Session 2			For Sessions 2-4: To more closely match treatment duration and therapist time between groups, the Control group will have: 1. A longer re-assessment at the beginning of the session 2. Inactive ultrasound application
Assessment	Standard subjective and physical re-assessment	Brief subjective evaluation and re-cap of session 1	
Education	General education Discussion of x-ray findings (read interpretation section) Provide inactive ultrasound to 4 locations on the most painful knee (~5 mins each).	Enhanced education Discussion of x-ray findings (focus on normal age-related changes; positive reframing of structural findings)	
Graded walking program, goal-setting	Use baseline walking tolerance to calculate a 'start' walking level and set a walking program for the week ahead. Set activity goals (short and long term)		
Session 3			
Assessment	Standard subjective and physical re-assessment	Brief subjective evaluation and re-cap of sessions 1&2	
Education	General education Provide inactive ultrasound to 4 locations on the most painful knee (~5 mins each).	Enhanced education	
Graded walking program	Check in. Increase activity by 10% during the next week. Discuss general principles of activity pacing. Provide the Practical considerations of activity handout		
	N/A	Discuss and consider context when planning walking/activity this week	
Session 4			
Assessment	Standard subjective and physical re-assessment	Brief subjective evaluation and re-cap of sessions 1-3	
Education	General education Provide inactive ultrasound to 4 locations on the most painful knee (~5 mins each).	Enhanced education	
Graded walking program, goal-setting	Check in. Increase activity by 10% during the next week. Set-up walking and general activity plan over the next 4 weeks.		
	Discuss flare-ups and how to reduce activity.	Review flare-ups – what they mean (pain science) and the activity plan.	

Table 4: In-person treatment session by session breakdown for each group. US, Ultrasound; EP, Explain Pain; AA, Arthritis Australia

2. At-home treatment sessions (over 4 weeks, following in-person sessions):

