Statistical Methods

Baseline clinical and demographic characteristics of the participants will be reported using descriptive statistics. Patient eligibility, recruitment and retention rates will be calculated. Reasons for refused consent and study withdrawal will be recorded when possible. Questionnaire completion rates will also be calculated.

Change scores (and 95% confidence intervals) for pain, activity and function from baseline to follow-up will be reported. Estimates of treatment effect (and its variance) for the primary outcome measures planned for the subsequent RCT (pain VAS score and step count from accelerometry) will be used to assist calculation of an appropriately powered sample size for the larger trial.

Section 6. Methods: Monitoring

Data Monitoring – Interim Evaluation

Interim evaluation of the trial (led by the principal researcher) will occur after 1 month follow-up data has been received from 30% of participants. At this stage:

- Any issues/problems with participant recruitment procedures will be identified.
- Discussions will be held with the treating clinicians to seek feedback and concerns regarding
 - a. Feasibility of study procedures
 - b. Content of the interventions
 - c. Any other issues
- Collected data will be assessed for completeness
- Participant Experience Questionnaires will be reviewed for feedback regarding treatment credibility and acceptability.

Issues identified will be discussed with the clinical and research team (as appropriate) and any modifications to the study protocol or the intervention will be made and recorded. An external data monitoring committee is not needed since this is a low risk study and no data analysis will occur at the interim stage.

Harms

There are no anticipated risks or harms associated with this study. Any unanticipated adverse events will be documented and reported and managed appropriately.

Auditing

No auditing of the feasibility trial will occur.

Section 7. Ethics and Dissemination

Research Ethics Approval

This study has been approved by the Human Research Ethics Committee at the University of South Australia.

Protocol Amendments

Protocol modifications (prior to commencing the study or at interim stage) will be communicated with the human research ethics committees at the University of South Australia and the clinical trials registry (ANZCTR).

Consent

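### The Harms section foresees no harms and commits to recording only unanticipated adverse events, yet the sessions plan for activity flare-ups, so it is unclear whether flare-ups must be recorded

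*Protocol*

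**What the plan says.** The recording rule is in the protocol, Section 6, Harms: "There are no anticipated risks or harms associated with this study. Any unanticipated adverse events will be documented and reported and managed appropriately". No other section of the protocol sets out how harms are documented.

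The intervention text in Section 3 foresees pain brought on by activity in several places:

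- **Graded walking program, both arms.** Participants "plan gradual weekly increases at a rate of approximately 10% each week".
- **Table 4, Session 1, both arms.** The instruction for the following week is "Establish baseline walking tolerance that does not result in sustained, increased pain following walking".
- **Table 4, Session 4, control.** "Discuss flare-ups and how to reduce activity".
- **Table 4, Session 4, Explain Pain.** "Review flare-ups – what they mean (pain science) and the activity plan".
- **Table 3 (educational topics), standard education.** Participants hear that "It is normal to feel some pain in your muscles when you start an exercise program or new activity", and are then told what to consider "if pain feels unusual or severe, or lasts for more than 2 hours after you have stopped".
- **Table 3 (educational topics), Explain Pain.** The matching message is "It is often not necessary to stop an activity if it is painful".

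**The concern.** The Harms section and the session content do not agree on whether any harm is expected. This matters because the recording commitment depends on that distinction: only unanticipated events are promised a record. An event that the sessions themselves prepare participants for is hard to call unanticipated.

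A pilot of this kind should tell the main trial what to expect. If flare-ups are treated as expected and left out, the report could say that no adverse events occurred when it means that no unexpected ones did. The two arms also hear different messages about pain during activity, so how often flare-ups occur could differ between them, and the main trial's safety plan would have nothing to draw on. Events not captured at the time cannot be recovered by an analysis plan written later.

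**Working it through.** No harm rate, safety threshold or safety sample size is stated, so there is no figure to reproduce. The check sets the passages side by side.

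**Step 1: what the rule covers.** The two sentences of the Harms section can be read in two ways.

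- *Reading A.* Nothing is anticipated, so every adverse event is unanticipated and must be recorded.
- *Reading B.* Events foreseen elsewhere in the protocol are anticipated, so the commitment does not reach them.

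**Step 2: which reading the rest of the protocol supports.** Reading A needs the set of anticipated events to be empty. Table 4 names flare-ups in both arms, and its Session 1 instruction treats lasting pain after walking as something to look out for. The educational topics table foresees unusual, severe or prolonged pain in the control material. The set is not empty, so Reading A conflicts with Section 3. Reading B follows the literal wording, but nothing in the protocol states outright that expected events are to be left out.

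**Step 3: who applies the rule.** Under *Treating physiotherapists* in Section 3, each physiotherapist delivers only one of the two interventions. If one reads the sentence as A and another as B, the difference in reading coincides with the difference in arm.

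**Step 4: whether anything else counts flare-ups.**

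- *Forms.* The list in Section 5 (Appendices 3 to 18) has no adverse event or flare-up form.
- *Home diary.* It is described as a record of completed workbook tasks and walking goals.
- *Weekly calls.* They follow progress over the four home weeks; no harm question is specified.
- *Pain VAS.* It asks for the average over the past week, at baseline and weeks 4, 8 and 26. The three follow-up ratings cover 3 of 26 weeks (3/26 = 11.5%), and 2 of the 8 weeks up to the end of treatment. An average does not identify an episode.
- *WOMAC pain.* Taken at the same visits, it is a score, not an event count.
- *Session re-assessments.* They occur in Sessions 2 to 4 in both arms, but Table 4 makes them longer in the control arm and brief in the Explain Pain arm, with no harm item in either.
- *Experience and short-answer forms (Appendices 16 to 18).* None has a harm item.
- *Progression criteria (Table 5).* None concerns harms.

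Several of these could bring a flare-up to light. None turns it into a counted event.

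**Step 5: what a count could show.** The target is 20 to 30 participants at 1:1, so 10 to 15 per arm. Exact (Clopper-Pearson) 95% limits for x of n run from the 0.025 quantile of Beta(x, n − x + 1) to the 0.975 quantile of Beta(x + 1, n − x). For invented counts, used only to show precision:

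| Participants with an event | 95% interval |
|---|---|
| 2 of 10 | 3% to 56% |
| 4 of 10 | 12% to 74% |
| 3 of 15 | 4% to 48% |
| 6 of 15 | 16% to 68% |

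The intervals overlap heavily. Counts of this size describe; they do not compare.

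**The case against.** The best defence is Reading A: the sentences stand next to each other, the section says nothing is anticipated, and so any adverse event qualifies for recording. A discussion of flare-ups is self-management education for people enrolled with long-standing pain of at least 40 mm, and need not mean that a flare-up is an adverse event. Some muscle soreness on starting exercise is described as normal. Flare-ups can also surface through the pain scores, re-assessments, audio-recorded sessions, weekly calls, recorded reasons for withdrawal, the interim discussion with clinicians and the closing interview. Harms are not an objective of this small feasibility study, and no decision in Table 5 depends on them.

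Much of this stands. Exclusion is one of two readings, and flare-ups are not invisible. What does not stand is that the wording is therefore harmless: Reading A contradicts Section 3, and none of the other routes produces a count. A later analysis plan could define terms, but could not supply events never recorded.

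A reader might infer more than the protocol supports:

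- *That flare-ups will certainly go unrecorded.* The text permits that; it does not require it.
- *That flare-ups are the most likely harm, or occur at some given rate.* No rate or ranking is given.
- *That the rule itself favours one arm.* The wording is the same for both; a difference could arise only from how separate therapists read it.
- *That falls and injuries are also foreseen.* The Harms section and the session content name neither as an expected event.
- *That participants or the ethics committee were misinformed.* The consent materials were not available for this review, so nothing can be inferred from them.

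**Conclusion.** The point holds as an internal contradiction in a rule that governs prospective data. The Harms section denies any anticipated harm and limits its commitment to unanticipated events, while Section 3 plans for flare-ups and lasting pain after activity in both arms. On a literal reading flare-ups need not be recorded; on the kindest reading the rule is ambiguous for therapists who are separate by arm.

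The size cannot be put as a number, because the protocol gives no flare-up rate and none is assumed here. The consequence is confined to harms reporting and what it passes on to the main trial; the feasibility criteria are unaffected. The conclusion rests on reading the planned flare-up content as evidence that the protocol anticipates such events. It does not depend on how often they occur or on how they should be managed.

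**What to change.** Reconcile the Harms section with Tables 3 (educational topics) and 4:

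1. Delete the opening sentence of the Harms section and the word *unanticipated* from the second.
2. State that all adverse events, expected or not and including activity-related pain flare-ups, are documented and reported descriptively by arm: participants with at least one event, and number of events.
3. Add one identical line to the session and weekly-call records in both arms, and one item to the existing week 8 and week 26 questionnaires. The questionnaire items are needed because in-person sessions and calls end by week 8.

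The cost is a slightly longer record, two added questionnaire items and a higher reported event count. The week 26 item looks back over 18 weeks (26 − 8), so it will depend on recall. With 10 to 15 per arm the counts should be presented without any claim about a difference between arms. The change concerns recording and reporting only; it proposes no rule for managing flare-ups.

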At the completion of the 4 in-person sessions, participants in both groups will receive weekly individualised walking goals that aim to promote a graded activity progression. During the 4 weeks of at-home treatment activities, the treating clinician will call participants 1x/week to check in and follow their progress. A home diary will be used to record workbook/walking goal completion; our work has shown that diary use increases compliance.²⁸

Explain Pain Group

Participants will be asked to complete tasks at home which will involve using the Protectometer handbook to identify the unique safety and danger cues that are present for activity tasks and that may influence pain levels during activity.

Standard education and Sham control Group:

Participants will receive a workbook that includes information and questions about the known benefits of activity, health risk of inactivity, and the relevance to OA. They will complete sections of this workbook over the 4 weeks.

Treating physiotherapists:

Different physiotherapists will provide each intervention, with each physiotherapist providing only one of the interventions. Use of physiotherapists specific to each treatment group will be used to minimise participant un-blinding and to reduce therapeutic cross-over between intervention groups (i.e., it may be difficult to not discuss Explain Pain principles once trained). Each treating physiotherapist will receive group-specific training by the study researchers. The therapist providing Explain Pain will receive additional training via the Noigroup Explain Course. The treatment sessions of both groups will be audio recorded to evaluate intervention fidelity.

Outcomes

Primary Outcomes:

The primary outcome of this study is to pilot and to assess the feasibility of successfully conducting a large RCT that investigates the effect of adding Explain Pain (vs adding sham treatment) to an individualised, physiotherapist-led physical activity and general education program in adults with painful knee OA – through the evaluation of pre-specified feasibility criteria.

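### The Harms section anticipates no harms and commits to recording only unanticipated adverse events, but the session plan foresees flare-ups in both arms, so whether flare-ups are recorded is undetermined and nothing asks about them

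*Protocol*

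**What the plan says.** Section 6, Harms, consists of two sentences. The first is a premise: "There are no anticipated risks or harms associated with this study". The second is the recording rule: "Any unanticipated adverse events will be documented and reported and managed appropriately". The paragraph does not define an adverse event, say who documents it or say how it is elicited.

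The intervention text in Section 3 foresees activity-related pain:

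- Both arms follow a graded walking programme. Participants start 20% below the distance or time at which their pain increases, and then "plan gradual weekly increases at a rate of approximately 10% each week".
- Table 3 (educational topics), control arm: "It is normal to feel some pain in your muscles when you start an exercise program or new activity". It goes on to cover pain that is unusual, severe or prolonged.
- Table 3 (educational topics), Explain Pain arm: "It is often not necessary to stop an activity if it is painful".
- Table 4, session 4, control arm: "Discuss flare-ups and how to reduce activity".
- Table 4, session 4, Explain Pain arm: "Review flare-ups – what they mean (pain science) and the activity plan".

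During the four at-home weeks, "the treating clinician will call participants 1x/week to check in and follow their progress". Each physiotherapist delivers only one of the two interventions and, according to the Blinding section, knows the allocation.

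**The concern.** A rule limited to unanticipated events works only if the reader knows which events are anticipated. The Harms paragraph implies that none are, while the session tables plan for flare-ups and for pain on starting activity. A clinician who has just taken a participant through the session 4 flare-up topic could reasonably treat a later flare-up as expected and not document it. Another clinician, reading the Harms paragraph alone, could document the same event. Because therapists are arm-specific, such a difference in reading could line up with treatment arm.

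What is at stake is how far the pilot's safety information can be interpreted. The study is meant to rehearse the main trial's procedures. A low harms count obtained without a definition and without asking would say little about the walking programme, and a difference between arms could reflect reporting rather than experience.

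**Working it through.** The protocol gives no harms figure to reproduce, so the check is mainly a comparison of passages.

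**1. Is a flare-up anticipated?** By the Harms paragraph, no: it declares the set of anticipated harms empty. By Table 4, yes: flare-ups are planned content in both arms. The two statements need reconciling.

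**2. Is a flare-up recorded under the rule?** Two readings are open.

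- Taking the Harms paragraph alone, nothing is anticipated, so every adverse event is unanticipated and is recorded, flare-ups included.
- Taking it with Tables 3 and 4, a flare-up is foreseen and falls outside the commitment.

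The text does not choose between them. Falls and new injuries are not foreseen anywhere in the session plan, so the rule covers them on either reading.

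**3. Does any instrument ask?**

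| Place | What it collects | Harms item |
|---|---|---|
| Section 5, list of forms (Appendices 3-18) | Screening, pain, function, beliefs, mood, experience | None listed |
| Visit schedule (the second table numbered 3) | Measures, questionnaires, treatment sessions | No row |
| Home diary | Completion of workbook and walking goals | None |
| Appendix 16 | Ten statements on credibility, acceptability and usefulness | None |
| Appendix 17 | Four open questions on likes, dislikes and improvements | None direct |
| Table 5 | Progression criteria | None |

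**4. How much would the pain outcomes catch?** The Pain VAS form asks about the past week and is collected after baseline at weeks 4, 8 and 26. Three one-week windows cover 3 of 26 weeks, leaving 26 - 3 = 23 outside any window. Of the four at-home weeks (week 4 to week 8), only the last falls in a window. The VAS items are weekly averages, and results are reported as change scores, so a short flare-up can be averaged out even inside a window. The WOMAC form as printed states no recall period.

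**5. When does the planned walking level pass the starting tolerance?** With tolerance set to 1.00, the start is 0.80. Successive 10% increases give 0.80 x 1.1 = 0.88 (after session 3), 0.88 x 1.1 = 0.968 (after session 4) and 0.968 x 1.1 = 1.065. If weekly increases continue and tolerance does not change, the nominal level first exceeds baseline tolerance at the third increase, in the home phase. This indicates timing only, since tolerance may itself rise. It does show that the weeks with the least outcome coverage are not those with the lowest load.

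**6. Could ascertainment differ by arm?** In the home phase the regular contact is the arm-specific, unblinded clinician, and the two arms are taught different things about painful activity and flare-ups. Unprompted mention by participants, and its classification by clinicians, could therefore differ. The protocol does not say who documents adverse events, so this is a possibility and not a demonstrated bias.

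**The case against.** The strongest reply is that the Harms paragraph is coherent when read alone: with no harms anticipated, every adverse event is unanticipated and must be documented. On that reading nothing is excluded. This stands as far as it goes. A reader might infer that flare-ups are left out of the safety record, or that the pilot would report almost no harms whatever happened. The documents support neither: flare-ups have an undetermined status, and falls or new injuries are recordable on either reading. Nor does the protocol rank harms, so it does not support calling flare-ups the most likely one. It gives no flare-up rate, so any count of missed events would rest on a figure from outside the document.

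Other parts of the reply also have force.

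- The programme starts below each person's tolerance, and some muscle pain on starting exercise is not in itself an adverse event.
- Worsening pain is not wholly unrecorded. VAS and WOMAC are collected in the same way in both arms, reasons for withdrawal are noted when possible, and clinicians' concerns are sought at the interim evaluation.
- Harms are not an objective or a progression criterion, and no progression decision in Table 5 depends on them.
- The consent materials were not available, so what participants are told about reporting problems cannot be judged.

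These points limit the weight of the concern. They do not resolve the ambiguity in the rule or supply a question that elicits harms.

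**Conclusion.** The concern holds as an inconsistency with a practical consequence. The Harms section and the intervention tables disagree on whether any harm is anticipated; the recording rule depends on that answer; and no listed form, scheduled question or visit-schedule row elicits harms. The indirect information from pain scores is real but partial: the VAS windows cover 3 of the 26 weeks. Different reporting by arm is possible but not shown.

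The weight is minor to moderate. The study is small and low-risk, and the benefit of a change lies in safety information that can be interpreted by arm and carried into the main trial. The conclusion assumes that the visible list of forms is complete and that the removed consent materials do not contain a structured harms question. It takes no view on which arm's advice about painful activity is right.

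**What to change.** 1. Reconcile the Harms paragraph with the educational-topics table and with session 4 of Table 4, so that the protocol gives one answer on whether activity-related pain and flare-ups are anticipated.
2. Replace the recording rule with a statement that all adverse events, expected or not, are recorded in both arms and tabulated by arm. Include activity-related pain flares, using a definition set by the investigators in advance. A definition is needed because participants enter with pain of at least 40 mm.
3. Add one identically worded, participant-completed adverse-event question to the existing week 4, 8 and 26 forms, with a matching row in the visit schedule.

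The cost is a wording change and one question on forms already in use. There are three limits. The harms count may look less favourable than under unprompted recording. The week 26 question asks for recall over 26 - 8 = 18 weeks. And an identical question reduces, but does not remove, the effect of the arms being taught different meanings of a flare-up.
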